Randomized trial of holding vs. continuing incretin-based therapies before upper endoscopy

Principal Investigator:

[name].

Email: [contact]

Address: [name]

Background:

Incretin-based therapies include GLP-1 receptor agonists (GLP-1RAs) and dual GLP1-RA and gastric inhibitory polypeptide (GIP) agonists. These drugs are commonly prescribed for diabetes and more recently, their use has risen exponentially as a primary therapy for weight loss. These medications can decelerate gastric emptying and diminish bowel motility by inhibiting peristalsis at the GLP-1 receptors situated in myenteric neurons. Therefore, there exists a theoretic potential for gastroparesis, retained gastric contents, perioperative regurgitation, and pulmonary aspiration syndrome, and this is a concern for anesthesiologists and patients taking these medications.

The American Society of Anesthesiologists recently released a consensus-based statement that recommends patients on daily dosing hold incretin-based therapy the day of the procedure, and those on weekly dosing hold the medication a week before the procedure. The evidence for these recommendations is based on retrospective studies and case reports, and therefore the conclusions may be overly prescriptive. Furthermore, holding incretin-based therapy poses a risk for worsening diabetes control and more importantly, could cause unnecessary delays in care if a patient's procedure is postponed because they failed to hold the medication based on the recent recommendations (1-3).

Study Objective:

To assess whether holding incretin-based therapy before endoscopy reduces the likelihood of clinically relevant Residual Gastric Volume (RGV).

Hypothesis:

Holding incretin-based therapy is non-inferior to continuing incretin-based therapy for reducing the risk of clinically relevant RGV.

Study design:

Randomized Non-Inferiority Controlled Trial.

Blinding:

Single-blind: endoscopist and anesthesia team will be blinded to study group assignment.

Primary Outcomes:

The primary outcome is clinically significant residual gastric volume defined as a composite of the following variables:

- Residual gastric volume that precludes adequate endoscopic examination
- Residual gastric volume that necessitates premature termination of the endoscopy procedure
- Need for endotracheal intubation due to stomach contents.

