- Occurrence of aspiration events requiring extended observation/monitoring, unplanned therapeutics, and/or hospital admission

Secondary Outcomes:

- Presence of any solid food
- Presence of moderate liquid content
- Increased RGC defined as any amount of solid content or $> 0.8 \text{ mL/Kg}$ of fluid content (measured from the aspiration/suction canister).
- Aspiration events up to 48 hours after endoscopy
- Differences in primary and secondary outcomes between different medications

Inclusion Criteria:

- Patients using incretin-based therapies at a stable dose for more than 1 month.
- Understand the study procedures and will be able to provide written informed consent to participate in the study.
- Patients scheduled for outpatient esophagogastroduodenoscopy (EGD), combined EGD and colonoscopy, endoscopic ultrasound (EUS), or endoscopic retrograde cholangiopancreatography (ERCP) under monitored anesthesia care (MAC) or moderate sedation.

Exclusion Criteria:

- Documented history of gastroparesis (based on a 4-hour solid-phase gastric emptying study)

- Known history of achalasia
- Surgical or genetically altered foregut anatomy
- Known gastric outlet obstruction or pre-procedure imaging suggestive of gastric outlet obstruction.
- Patients who did not follow the standard NPO (nil per oral) instructions.
- Patients who have planned endotracheal intubation (ETT) during their upper endoscopy procedure (EGD, EUS, or ERCP).
- Ongoing opiate use
- Unable or unwilling to give written consent

Randomization:

- Patients will be randomly assigned to either continue incretin-based therapy as prescribed (“continue” group) or to hold therapy as outlined in the ASA guidance recommendations (“hold” group).
- Simple randomization will be applied post-enrollment, utilizing REDCap serial numbers with pre-determined interventions (“continue” vs. “hold”). The randomization table of allocation will be completed by a statistician on REDCap to ensure concealed allocation.

Study Operation:

- The candidates for the study will be determined either during the gastroenterology clinic visit OR based on review of records by a member of the research team of patients scheduled for upper endoscopy, EUS, and ERCP cases three to four weeks in advance
- Patients’ invitation
 - For patients who are scheduled for the procedure through the gastroenterology clinic, the patient’s clinic provider will invite the patient for the study during the office visit or with a phone call.

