 - For patients who are not scheduled via the above route, a letter of invitation will be sent to the patient from the physician completing the procedure through the US mail or MyChart.
- Patient consent
 - Interested patients in the clinic setting will be given the option to complete a research encounter during the same day, including in-person consent if interested, or complete the process remotely over the phone and through MyChart Electronic consent, or DocuSign.
 - Patients who are not identified in clinic but through chart review will receive a phone call and phone encounters will be completed with interested potential participants and will include an explanation of the study and the consent process (phone scripts attached). MyChart Electronic consent process or DocuSign will be used to send the study consent to the participants.
- After obtaining consent, the patient information will be entered into the REDCap which will give the patient a REDCap serial number.

- A randomization tool in the REDCap will determine the intervention (The randomization table of allocation will be completed by a statistician on REDCap to ensure concealed allocation).
- The patient will be informed about the intervention during the clinic visit by a study member (not the endoscopist) or over the phone.
- A few days before the intervention, the patient will receive a call as a reminder of the intervention and instruction from a study member (not the endoscopist).
- On the endoscopy day, the proceduralist and anesthesia team will be blinded to the patient's group assignment. To ensure that blinding is maintained, a sticker will be placed on the patient physical chart to remind the provider to avoid asking about the study intervention.
- A research coordinator/investigator will confirm intervention compliance and record the variables of interest for the study.
- Information will be directly entered into the Redcap data collection sheet or recorded on a physical paper-based collection sheet and transferred immediately to Redcap on the same day. The physical sheets will be shredded on the day of the procedure.
- A phone call to the patient within the first week after the procedure to follow up and exclude aspiration events. If patient cannot be contacted, then a member of the study team will review patient records to identify any emergency department visits or hospitalizations related to a post-procedure aspiration event.

Electronic Consent operation

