Date of birth, gender, race, body mass index (BMI), type of incretin-based therapy used, incretin therapy dose, pre-endoscopy clinical symptoms, presence of diabetes, last HbA1c if available, detailed endoscopic reports, gastric residual content on endoscopy, and RGC-related events as described above. Please refer to the data collection sheet for details of the variables above.

Study Statistics

The Statistics will be done with the help of a Cleveland Clinic statistician. Data will be extracted in deidentified form directly from Redcap for analysis.

Once data has been collected, we will use STATA version 14.1 (STATA Corp, College Station, TX, USA) for statistical analysis. We will use statistics of central tendency (mean, median, and mode) for most values. Data normality will be tested using Kolmogorov-Smirnov test. We will use Pearson’s chi-square tests for categorical variables and T-test for continuous variables. A P-value of < 0.05 will be considered significant for all statistical analyses. The primary outcome will be calculated using chi-square or Mann-Whitney test. For the primary outcome, an intention-to-treat analysis will be utilized.

Interim Analysis and Data Monitoring Committee (DMC)

The study DMC will include the following: The gastroenterology program director at Weston, a gastroenterologist, and a Cleveland Clinic statistician. Meetings will be held at 20%, 50, and 100% of recruitment to ensure data security compliance, appropriate rate of recruitment, and study adverse events monitoring. A report of each meeting will be sent to the IRB. The DMC will not be blinded for study groups. Interim analysis will be conducted after 20 and 50% of recruitment on the second DMC meeting, and the study will be stopped if inferiority is confirmed.

Data Security

Data, including patient information and consent, will be stored electronically in the Redcap system\DocuSign which is password-protected and on the secure Cleveland Clinic network. If physical paper sheets were used, the physical paper sheets' information would be transferred to Redcap and shredded on the day of data gathering.

Possible Harm to Subjects and Adverse Events

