The study risk is related to continuing incretin-based therapy in the periprocedural time. Medication continuation has a theoretical risk of increased residual gastric content, although there is no strong evidence to support that. Increased gastric residual content can lead to prolonged monitoring time, increased procedure time, premature termination of the procedure, unexpected urgent endotracheal intubation, or aspiration events.

Breach of confidentiality is another potential harm, and it will be minimized by the data security plan described above. The study does not involve prescribing incretin-based therapy.

All serious unexpected adverse events will be recorded and reported to the IRB in a timely fashion. Adverse events (study outcome) will be reported to the IRB after each DMC meeting.

References

- 2- Silveira SQ, da Silva LM, de Campos Vieira Abib A, et al. Relationship between perioperative semaglutide use and residual gastric content: A retrospective analysis of patients undergoing elective upper endoscopy. *J Clin Anesth.* 2023;87:111091. doi:10.1016/j.jclinane.2023.111091

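### Worsening diabetes control is named as a risk of holding therapy, but the risk section omits it and nothing described systematically records anticipated or non-serious glycaemic worsening in either arm

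*Combined protocol and SAP*

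**What the plan says.** All places are in the combined protocol and SAP.

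- **Background:** "holding incretin-based therapy poses a risk for worsening diabetes control". This is part of the argument for running the trial.
- **Possible Harm to Subjects and Adverse Events:** "The study risk is related to continuing incretin-based therapy in the periprocedural time". The one other item is "Breach of confidentiality is another potential harm". Events that are both serious and unexpected are recorded and sent to the IRB. The remaining adverse events reported after DMC meetings are equated with the study outcomes.
- **Randomization and Sample Size Determination:** patients are randomised to continue, or to hold as in the anaesthesiology society's guidance. Hold is labelled the experimental group, with 60 patients per arm.
- **Primary Outcomes:** "The primary outcome is clinically significant residual gastric volume defined as a composite of the following variables". Its components concern residual volume, intubation and aspiration. The secondary outcomes are gastric content, "Aspiration events up to 48 hours after endoscopy", and differences in these outcomes between drugs.
- **Study Variables:** the glycaemic items are "presence of diabetes, last HbA1c if available".
- **Study Operation:** "A phone call to the patient within the first week after the procedure to follow up and exclude aspiration events". If the patient cannot be reached, records are searched for aspiration-related emergency visits or admissions.
- **Interim Analysis and DMC:** an unblinded DMC monitors adverse events at 20%, 50% and 100% of recruitment.

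**The concern.** The protocol uses a glycaemic cost of holding to justify the trial, then leaves that cost out of its statement of study risk and its described data collection. Two things are at stake. First, the risk statement put to the IRB is inconsistent with the Background. Second, the trial can show what holding gains in gastric content and aspiration, but has almost nothing to say about what it costs in diabetes control. If the result favours holding, an empty column for glycaemic harm could be read as absence of harm when nobody looked for it.

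**Working it through.** The point is textual, so the main check is to go through every route by which a glycaemic event after randomisation could enter the data.

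| Route | What it seeks, as described | Captures anticipated or non-serious glycaemic worsening? |
|---|---|---|
| Primary outcome | Residual volume, intubation, aspiration | No |
| Secondary outcomes | Solid or liquid content, aspiration to 48 hours, differences by drug | No |
| Study Variables | Diabetes status, last HbA1c if available, gastric-content events | No. No measurement after the intervention is listed, and a last available HbA1c cannot show the effect of a hold lasting a day to about a week |
| Follow-up call | Aspiration | No |
| Chart-review fallback | Aspiration-related visits and admissions | No. A visit for hyperglycaemia is outside the stated search |
| Adverse-event rule | Serious and unexpected events; study outcomes | No. Worsening control is foreseen in the Background, so it is hard to class as unexpected, and no study outcome is glycaemic |
| DMC | Adverse events at three looks | Only what the routes above supply |

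The Background's other complaint, that the guidance "could cause unnecessary delays in care if a patient's procedure is postponed because they failed to hold the medication", concerns patients who did not hold. It is not a harm of being assigned to hold and is not counted here.

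**The denominator.** The plan's figure of 60 per arm reproduces with the Farrington-Manning formula, taking 7% for continue, 0.5% for hold, a 3-point margin, one-sided 5% and 80% power. The restricted rates under the null are 0.0658 (hold) and 0.0358 (continue).

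- s0 = √(0.0658×0.9342 + 0.0358×0.9642) = 0.310
- s1 = √(0.005×0.995 + 0.07×0.93) = 0.265
- n = [(1.645×0.310 + 0.842×0.265) / (0.07 − 0.005 + 0.03)]² ≈ 60 per arm (power 0.804)

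This confirms the 60 but has no bearing on the point itself.

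**Patients concerned.** The documents give no diabetes share. Assuming 30–70%: 60 × 0.30 = 18 and 60 × 0.70 = 42 hold patients. This counts daily and weekly users together. By the Background's summary of the guidance, daily users hold on the procedure day and weekly users for a week. The mix is not given, so the number with a week-long hold is smaller by an unknown amount.

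**What collection could show.** With zero events in n patients, the one-sided 95% upper bound is 1 − 0.05^(1/n): 4.9% for n = 60, 6.9% for n = 42 and 15.3% for n = 18. The chance of seeing at least one event at an assumed true rate of 5% is 1 − 0.95^n: 95%, 88% and 60% respectively.

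For a between-arm comparison at assumed rates of 5% versus 15% (two-sided 5%, arcsine approximation), the effect size is h = 2·asin√0.15 − 2·asin√0.05 = 0.344, and power is Φ(h√(n/2) − 1.96). That gives 18% for 18 per arm and 35% for 42 per arm. The data would therefore be descriptive. As planned, no estimate is possible.

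**The case against.** The best defence is that holding follows published guidance, so the harm section may be read as listing only the risk added by departing from it. This does not go far. Holding is assigned by randomisation, the protocol itself labels it experimental, and the Background questions the evidence behind the guidance.

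A second defence is that the stated objective is clinically relevant residual gastric volume, and that a reason given in the Background need not become an endpoint. That is fair: the primary estimate and its validity are untouched. It does not explain why a risk stated in one section is missing from the section meant to list risks.

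Third, there is a safety net: serious unexpected events are recorded whichever arm they occur in, and a DMC reviews adverse events. This stands, and it limits the point to anticipated or non-serious events.

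Fourth, the data collection sheet, phone scripts and consent form could contain more. This also stands as a limit. However, Study Variables refers to the sheet for details of the variables it lists, and those include no glycaemic measure after randomisation.

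Finally, small numbers and unblinded self-report make any comparison weak. That is true, and it is why only descriptive reporting is suggested.

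**Conclusion.** The point holds in a limited form. The Background and the harm section disagree about whether holding carries a clinical risk, and no described procedure systematically ascertains anticipated or non-serious glycaemic worsening in either arm. It concerns perhaps 18–42 of the 60 hold patients, on an assumed diabetes share of 30–70%, with daily and weekly dosing combined. It affects the risk statement and what the trial can say about the cost of holding, and leaves the primary analysis alone.

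A reader might infer more than the documents support:

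- **That hold-arm harm cannot be detected at all.** A serious unexpected event would be recorded and is within the DMC's remit.
- **That follow-up differs between arms.** Gastric and aspiration outcomes are sought in the same way in both. The gap is in the type of event sought.
- **That all hold patients with diabetes go about a week without therapy.** The guidance as summarised gives daily users a hold on the procedure day only.
- **That participants are not told of the risk.** The consent form was not available, so this cannot be judged.

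**What to change.** 1. Reconcile the Background with the harm section by listing worsening diabetes control as a risk of the hold arm. Check that the consent form agrees, and amend it only if it does not.
2. In both arms, for patients with diabetes, extend the planned follow-up call and the chart-review fallback to record glucose excursions, unscheduled care or added glucose treatment since randomisation, and the date therapy was resumed (or that it had not been by the time of the call). Record a pre-procedure glucose only where one happens to be available; the protocol does not mention a routine check.
3. Report these by arm, separately for daily and weekly dosing, as a descriptive secondary safety outcome, and include them in the DMC reports.

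The cost is a few REDCap fields, two or three questions in a call already planned, a wider chart search and a protocol amendment. No visit or test is added. The downside is that self-report is incomplete and patients know their assignment, so reporting may differ by arm; the comparison is unpowered and should be labelled so. No change to how therapy is held or resumed is proposed.

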- An investigator or research coordinator will contact the invited candidates over the phone 2-4 weeks before the scheduled procedure. The study purpose, intervention, adverse events, and consenting process will be discussed over the phone. The encounter will be documented in the patient chart as a phone encounter.
- Subjects interested in the study will be provided with consent through MyChart Electronic consent or DocuSign with instructions to complete online consent signing.
- After all parties complete the consent, a randomization of the study intervention will be done through Redcap.
- A follow-up phone call will be made to communicate the instructions to the participants.

Rational for electronic consent (E-consent)

The study is not feasible with conventional consent, especially for open access procedures for the following reasons:

- The duration for participant involvement in the study is short, and the study intervention is only applied one week before the procedure, which would make it impractical to bring the patient for an extra encounter and would decrease the chance for enrollment.

- Many procedures are scheduled in an open-access fashion, which means that the patient is scheduled for the procedure by a provider other than the performing physician and/or from a different department.
- The intervention for the study must be completed one week before presenting to the procedure, which requires that the patient be enrolled before the procedure date.

Sample Size Determination:

- Previous retrospective studies indicate that 5-7% of GLP-1RA users have increased RGV compared to less than 0.5% in non-users.
- If there is a significant difference in favor of the experimental (“hold”) group of 7%, then 120 patients are needed (60 in each group) to be 80% certain that the upper limit of a one-sided 95% confidence interval (or equivalently a 90% two-sided confidence interval) will exclude a difference in favor of the standard group of more than 3% (the non-inferiority limit) using Farrington-Manning’s score test.
- Because estimates from previous retrospective studies are for the outcome of residual gastric volume, they may not accurately reflect our primary outcome, which is a more pragmatic and clinically useful outcome. Therefore, we plan to conduct an interim analysis at 20% recruitment and may adjust sample size if necessary, based on point estimates derived from the interim analysis.

Study Variables

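### The plan does not say that serious aspiration or intubation counted as a study outcome is reported promptly, and no DMC meeting or event-triggered review is planned while the second half is recruited

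*Combined protocol and SAP*

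**What the plan says.** Under Possible Harm to Subjects and Adverse Events, two adjacent sentences govern reporting to the IRB. The first is "All serious unexpected adverse events will be recorded and reported to the IRB in a timely fashion". The second is "Adverse events (study outcome) will be reported to the IRB after each DMC meeting". The word *unexpected* is not defined, the first sentence sets no time limit, and the second makes no exception for serious events.

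The same section lists the foreseeable consequences of increased gastric content. Aspiration is on the list, and so is urgent intubation, to which the section attaches the word *unexpected*. Both are components of the composite under Primary Outcomes. The aspiration component expressly includes cases that lead to hospital admission.

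Under Interim Analysis and Data Monitoring Committee (DMC), the schedule is: "Meetings will be held at 20%, 50, and 100% of recruitment to ensure data security compliance, appropriate rate of recruitment, and study adverse events monitoring". Each meeting produces a report to the IRB. Interim analyses, with stopping if inferiority is confirmed, are tied to 20% and 50% of recruitment. No unscheduled meeting, no trigger based on a single event and no individual notification to the committee is described.

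**The concern.** The harms section states that the trial's risk comes from continuing therapy up to the procedure. Aspiration with admission is thus the main harm the trial has to watch, and it is also an outcome. If *unexpected* is taken to mean not foreseen in the protocol, such an event fails the test for timely reporting and falls under the outcome sentence. Staff could then follow the protocol to the letter and hold the report until the next DMC meeting.

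For an event in the 61st patient, that meeting is the one at 100% of recruitment. The information would exist much sooner: Study Operation has outcomes recorded on the day and a follow-up call within the first week to look for aspiration. The delay would come from the reporting rule, not from late detection. What is at stake is whether the IRB and the DMC could act on a serious event while patients are still being enrolled.

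**Working it through.** **1. The plan's sample size.** The number of patients between meetings depends on the total, so that figure is checked first. Sample Size Determination says "120 patients are needed (60 in each group", with power stated as "to be 80% certain", the criterion as the "upper limit of a one-sided 95% confidence interval (or equivalently a 90% two-sided confidence interval", and a 3-point margin under the Farrington-Manning score test. The cited rates are "5-7% of GLP-1RA users have increased RGV compared to less than 0.5% in non-users".

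Take hold 0.5%, continue 7%, margin m = 0.03, one-sided alpha 0.05, power 0.80, 1:1 allocation. The formula is

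n per arm = [(z₀.₉₅·s₀ + z₀.₈₀·s₁) / (m − (p_hold − p_cont))]².

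- Restricted estimates under a difference of +0.03: 0.0658 (hold) and 0.0358 (continue), so s₀ = √(0.0658×0.9342 + 0.0358×0.9642) = 0.310.
- Unrestricted: s₁ = √(0.005×0.995 + 0.07×0.93) = 0.265.
- Denominator: 0.03 + 0.065 = 0.095.
- n = [(1.645×0.310 + 0.842×0.265)/0.095]² ≈ 59.4, rounded up to 60 per arm, 120 in total (power 0.804).

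The figure reproduces. These rates differ by 6.5 points, whereas the text assumes 7; pairs exactly 7 points apart give 52 (0% and 7%), 57 (0.5% and 7.5%) or 62 (1% and 8%) per arm. The total of 120 is taken as stated.

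**2. Where the meetings fall.** 0.20×120 = 24; 0.50×120 = 60; 1.00×120 = 120. The gaps are 24, 36 and 60 patients. The last and longest gap, 120 − 60 = 60, is half the trial.

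**3. Which reporting route applies.**

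| Event | Named as a harm | Primary-outcome component | Called unexpected in the harms section | Route |
|---|---|---|---|---|
| Aspiration with admission | Yes | Yes | No | Outcome sentence, on a natural reading |
| Urgent intubation for stomach contents | Yes | Yes | Yes | Either sentence |

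**4. Chance that the gap matters.** The documents give no rate for serious aspiration or intubation, so the per-patient rate p, averaged over both groups, is an assumption. With independent patients, P(at least one in 60) = 1 − (1 − p)⁶⁰.

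| Assumed p | Calculation | P(at least one in 60) |
|---|---|---|
| 0.5% | 1 − 0.995⁶⁰ | 26% |
| 1% | 1 − 0.99⁶⁰ | 45% |
| 2% | 1 − 0.98⁶⁰ | 70% |

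**The case against.** The best defence is that the two sentences are cumulative: serious unexpected events go promptly, and all outcome events also appear in the report after each meeting. Nothing in the first sentence excludes an outcome event. Since the harms section itself calls urgent intubation unexpected, a serious intubation can take the timely route. This stands. A reader might infer that serious aspiration and intubation reach the IRB only after DMC meetings. The documents do not say so; for intubation the wording points partly the other way, and for aspiration the inference depends on the meaning of an undefined term. The reply is that a rule on which two careful readers can differ is itself a defect when the event is serious.

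A reader might also infer that the last 60 patients have no review that could protect them. That goes too far. Timely reporting of serious unexpected events runs throughout. The final meeting is at 100% of recruitment, not of completed procedures, and Electronic Consent operation puts first contact 2 to 4 weeks ahead of the procedure, so some patients may still be waiting. The same lag means that the 50% meeting may see outcomes from fewer than 60 patients. The documents quantify neither effect. The total may also change after the 20% interim, although half of any fixed total would still follow the 50% meeting.

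Finally, a reader might apply the planning rates to the last 60 and obtain 1 − 0.93³⁰ × 0.995³⁰ = 90%. The arithmetic is right but it measures the wrong event. Those are rates of increased residual volume, the 0.5% is an upper bound for non-users, and the plan itself warns that they may not reflect even the primary composite.

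**Conclusion.** The concern holds as a gap in the reporting and review rules. The plan does not ensure prompt reporting of aspiration with admission, and it leaves the route for serious intubation open. It schedules no DMC meeting and describes no event-triggered review between 50% and 100% of recruitment, a span of 60 patients at the planned total. Whether this would delay action on an actual event is a matter of chance. Over the assumed range of 0.5% to 2%, that chance runs from about one in four to about seven in ten, which is material throughout. The conclusion on routing rests on reading *unexpected* as not foreseen in the protocol, a natural reading but not the only one. The point does not affect the sample size, the endpoints or the primary analysis.

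**What to change.** - **Possible Harm to Subjects and Adverse Events:** reconcile the two sentences so that every serious adverse event is reported promptly to the IRB, whether or not it is expected or a study outcome. State the reporting time. If *unexpected* is kept anywhere, define it. The report after each meeting can remain for outcome events that are not serious and for cumulative tables.
- **Interim Analysis and Data Monitoring Committee (DMC):** send each aspiration with admission and each unplanned intubation individually to the existing committee when it occurs, and state that the committee may convene between scheduled meetings. The committee is already unblinded, so this does not change what it may see.

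The cost is protocol wording and a few extra individual reports. Rescheduling the third meeting, for example to about 75% of recruitment, is optional: no figure in the documents supports that point, 30 of 120 patients would still follow it, and the reporting changes do not depend on it.
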